2.1.2 Secondary Objectives

- Assess progression free survival of patients receiving pembrolizumab and Sylatron.
- Assess overall survival of patients receiving pembrolizumab and Sylatron
- Assess the objective response rate of patients receiving pembrolizumab and Sylatron combination therapy based irRECIST.
- Assess the safety and tolerability of combined pembrolizumab and Sylatron therapy.

Hypothesis:

We propose that a PFS of 24 weeks and an OS of 40 weeks is clinically meaningful in patients who receive the combination of pembrolizumab and Sylatron following failure on frontline therapy (due to cancer progression or intolerance of treatment).

2.1.3 Correlative/Exploratory Objectives

- Determine the effect of Sylatron on anti- programmed death ligand-1 (PD-L1) level, immune score as determined by the density of CD3 and CD8 in the tumor interior and invasive margin(s) of the tumor, and the clonality of the T-cell repertoire.
- Determine the effect of Sylatron on anti-cancer immunity by measuring proliferation of CD8+ T cells, Granzyme B+ cells and proliferation of tumor cells, and correlating these changes with clinical response as determined by RECIST 1.1.

Hypothesis:

Therapies that target the programmed death-1 (PD-1) receptor have shown unprecedented rates of durable clinical responses in a sub-group of patients with various cancer types [1-5]. Biomarkers in patient tumor that will predict response to anti-PD-1 therapy are being actively investigated. One mechanism by which cancer tissues limit the host immune response is via upregulation of PD-1 ligand (PD-L1) and its ligation to PD-1 on antigen-specific CD8+ T cells [6, 7]. Recent research has reported that tumor regression after therapeutic PD-1 blockade requires pre-existing CD8+ T cells that are negatively regulated by PD-1/PD-L1-mediated adaptive immune resistance [8]. We propose that Sylatron will increase the response of pembrolizumab by increasing the tumor infiltrating CD3 and CD8 cells, and the level of PD-L1 and PD-1 expression in immune cells and cancer cells. In this study, we will first test the effect of Sylatron on tumor infiltrating lymphocytes, the level of PD-1 and PD-L1 expression, and clonality of the T-cell repertoire by comparing the tumor biopsies from baseline and three weeks of Sylatron treatment. Then we will examine whether the change of tumor infiltrating lymphocytes, the level of PD-1 and PD-L1 expression from Sylatron treatment correlates with clinical response in patient treated with pembrolizumab and Sylatron combination therapy.

2.2 Endpoints

2.2.1 Primary Endpoint

- The objective response rate is the proportion of all subjects with confirmed PR or CR according to RECIST 1.1, from the start of treatment until disease progression/recurrence (taking as reference for progressive disease the smallest measurements recorded since the start of treatment).

2.2.2 Secondary Endpoints

- PFS defined as measurement from the date of registration until the criteria for disease progression is met as defined by RECIST 1.1 or death occurs. Subjects who have not progressed will be right-censored at the date of the last disease evaluation.
- OS is defined as the time of registration until death as a result of any cause.
- Objective response rate is defined as the sum of complete response (CR) + confirmed partial response (PR) and will be determined as per irRECIST.
- Grade 3 and 4 toxicities as defined by the NCI Common Terminology Criteria for Adverse Events (NCI CTCAE) v4.

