5.2 Pembrolizumab and Sylvatron Administration

Each cycle = 21 days or 3 weeks. Sylvatron will be administered at 200mcg subcutaneously every week for up to 12 weeks (3 weeks as single agent, and 9 weeks in combination of pembrolizumab) starting Cycle 1 Day 1. The dose of sylvatron may be reduced to 120mcg weekly, or 60mcg weekly if patients experience unacceptable toxicities at the higher dose levels. Patients will be premedicated with acetaminophen 500 to 1000 mg orally 30 minutes prior to the first dose of sylvatron and as needed for subsequent doses. Injection sites will be rotated. During the Cycle 1 Day 1 visit, subjects will be provided education on how to manage sylvatron injections at home.

Pembrolizumab will be administered intravenously as a 30 minute infusion at a dose of 200 mg every 3 weeks starting Week 4 (Cycle 2 Day 1). **All trial treatments will be administered on an outpatient basis.** On the days that sylvatron and pembrolizumab are given together, sylvatron should be administered prior to the pembrolizumab infusion.

Sites should make every effort to target infusion timing to be as close to 30 minutes as possible. However, given the variability of infusion pumps from site to site, a window of -5 minutes and +10 minutes is permitted (i.e., infusion time is 30 minutes: -5 min/+10 min). The Pharmacy Manual contains specific instructions for the preparation of the pembrolizumab infusion fluid and administration of infusion solution.

With concerns about toxicity while using long-term sylvatron, if no additional benefit is seen beyond 12 weeks of treatment on top of that expected from pembrolizumab alone, patients will discontinue sylvatron treatment after they have received 12 weeks of this therapy (3 weeks as single agent and 9 weeks in combination with pembrolizumab). Pembrolizumab should be continued in the absence of unacceptable toxicity (based on CTCAE v4) until disease progression-based on RECIST 1.1. In patients who had responded to the combination therapy, when patient shows disease progression while on single agent pembrolizumab treatment, sylvatron may be resumed at the discretion of the site investigator after discussion with the sponsor-investigator.

Medication Administration (Cycle = 21 days or 3 weeks)

Drug	Dose	Route	Schedule	Regimen Treatment Period	Cycle
Sylatron	200mcg	Subcutaneous injection	Q1W starting C1D1	Day 1, 8 and 15 of each cycle (weekly)	21 days

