11.1.4 Relatedness

AEs will be categorized according to the likelihood that they are related to the study drug(s). Specifically, they will be categorized using the following terms:

Unrelated	Adverse Event is not related to the study drug(s)
Unlikely	Adverse Event is doubtfully related to the study drug(s)
Possible	Adverse Event may be related to the study drug(s)
Probable	Adverse Event is likely related to the study drug(s)
Definite	Adverse Event is clearly related to the study drug(s)

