12.2.2 Definition of Secondary Endpoints

- PFS: defined as time from registration till the patient's disease progression or death from any cause whichever occurs first (those for whom event of progression or death not observed will be censored).
- OS: defined as time from registration till the patient's death from any cause (patient who are still alive at the end of the study will be censored).

- Objective response rate: defined as the proportion of subjects who achieve the best response (CR and PR) determined by irRECIST.
- Safety and tolerability of the combination of Sylatron and pembrolizumab as assessed by CTCAE v4. Will include patients' toxicity profile, adverse event, serious adverse event, serious adverse even leading to discontinuation of the treatment, death.

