12.4.2 Analysis Plans for Secondary Objectives

Progression free survival (PFS) and overall survival (OS) will be evaluated using the methods of Kaplan and Meier (1958). 95% confidence interval will be constructed for the estimated median PFS and OS. The exploratory objective response rate will be estimated with its 95% exact confidence interval. Safety summaries will be presented by the severity of the adverse event and by relationship to study drug. Descriptive statistics (minimum, maximum, mean median, standard deviation for continuous variables; counts, percentages for categorical variables) will be used in summarizing of all laboratory and safety parameters (adverse events, serious adverse events, adverse events leading to discontinuation, deaths) for all treated subjects.

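### Sections 2.2.2, 12.2.2 and 12.4.2 describe the safety endpoint inconsistently: 2.2.2 stops at Grade 4, 12.2.2 and 12.4.2 differ on discontinuations, and no summary is planned by treatment period

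*Combined protocol and SAP*

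**What the plan says.** Safety and tolerability of the combined therapy is a secondary objective (Section 2.1.2). Three later sections say how it will be measured or summarised.

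- **Section 2.2.2** has one safety bullet: "Grade 3 and 4 toxicities as defined by the NCI Common Terminology Criteria for Adverse Events (NCI CTCAE) v4". It gives no rate, denominator or counting rule.
- **Section 12.2.2** sets no grade limit and lists "toxicity profile, adverse event, serious adverse event, serious adverse even leading to discontinuation of the treatment, death" (the fourth item evidently means serious adverse event).
- **Section 12.4.2**, the analysis plan, covers adverse events, serious adverse events, "adverse events leading to discontinuation, deaths", all in treated subjects. It adds: "Safety summaries will be presented by the severity of the adverse event and by relationship to study drug".

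Three other places bear on the point. Section 5.2 gives Sylatron for up to 12 weeks, "3 weeks as single agent, and 9 weeks in combination of pembrolizumab", with pembrolizumab continuing afterwards. Section 11.1.4 describes one relatedness rating to the study drug or drugs, with no separate rating for each. Section 12.4 defines a Safety set that, read literally, requires a dose of each drug, and a Treated set that requires only some exposure.

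**The concern.** A toxicity endpoint that ends at Grade 4 leaves out the worst outcome. If each patient is classified by worst grade, someone who dies of a toxicity leaves the Grade 3-4 count, and the rate improves because of the death. Section 10.1.7 itself notes fatal immune-mediated events and fatal myocarditis with pembrolizumab, so Grade 5 is a recognised possibility.

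The discontinuation item matters because tolerability is part of the objective and patients can stop without a serious event. Table 4, for example, lists inability to tolerate the lowest Sylatron dose step as a reason for permanent discontinuation, with no seriousness condition. Section 12.2.2 also does not say which drug must be stopped, although the two drugs have separate rules in Sections 6.1 and 6.2.

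The regimen has three phases with different exposure, and the objective concerns the combination. Summaries by severity and a single relatedness rating cannot show in which phase the toxicity arose.

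Section 13.4 requires results for all secondary objectives to be posted, so it should be clear in advance which description governs.

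**Working it through.** **1. The plan's own figures.** The documents give no numerical safety target. The only design figures concern response, under the rule 3/16 then 11/44. The exact probability of passing both stages is the sum over x = 4 to 16 of Bin(x; 16, p) × P(Y ≥ 12 − x), with Y ~ Bin(28, p).

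- At p = 0.17 this is 0.0461 (stated 0.046).
- At p = 0.35 it is 0.8091, so the type II error is 1 − 0.8091 = 0.1909 (stated 0.191 in Section 12.3).
- Dropout: 44/0.96 = 45.8, rounded up to the stated 46.

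These reproduce, and nothing below changes them.

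**2. The three descriptions side by side.**

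| Element | 2.2.2 | 12.2.2 | 12.4.2 |
|---|---|---|---|
| Grade limit | 3 and 4 | none | none; by severity |
| Fatal events | outside the endpoint | death listed | deaths listed |
| Stopping treatment | not mentioned | serious events only | any adverse event |
| Population | not stated | not stated | all treated subjects |
| Split by treatment period | no | no | no |

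Grade 5 is therefore missing only from 2.2.2, and the limit to serious discontinuations appears only in 12.2.2.

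**3. Size of the Grade 4 cap.** Let x patients have worst grade 3 or 4, and d patients have worst grade 5, among n.

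- Grade 3-4 rate = x/n.
- Grade 3 or higher rate = (x + d)/n.
- Difference = d/n.

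With n = 44 and d = 1 the difference is 1/44 = 0.0227, or 2.3 percentage points per patient. With the 46 to be enrolled it is 1/46 = 2.2 points. This is a maximum. If a patient counts whenever any Grade 3 or 4 event occurred, someone with such an event before a fatal one stays in and the difference for that patient is zero. The plan does not say which counting applies.

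**4. Population.** Pembrolizumab starts at Cycle 2 Day 1, after 3 weeks of Sylatron alone. A patient who stops or dies in the lead-in has had no pembrolizumab. That patient is among the treated subjects of 12.4.2 but outside the Safety set of 12.4.

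**5. Treatment periods.** Suppose Sylatron stops at week 12 and no dose is missed. For 24 weeks of treatment, a length borrowed from the PFS benchmark purely as an illustration:

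- Sylatron alone: 3/24 = 12.5% of the time.
- Both drugs: 9/24 = 37.5%.
- Pembrolizumab alone: 12/24 = 50%.

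Over 52 weeks the share on both drugs is 9/52 = 17.3%. These are shares of time, not of events. They also depend on passages that need reconciling: Section 5.2 words the week-12 stop conditionally and allows Sylatron to be resumed, and footnote 7 of the study calendar has it continuing weekly. Longer Sylatron use would raise the share on both drugs.

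**The case against.** The strongest reply is that nothing important would go unreported. Sections 12.2.2 and 12.4.2 both name deaths, and the severity summary in 12.4.2 has no upper grade. Section 12.4.2 also takes in non-serious discontinuations, and the list in 12.2.2 is introduced as what safety will include, not as a limit. On this view 12.4.2 is an analysis plan and not a third definition, and what remains is loose wording. Much of this stands. What it does not do is make the formal endpoint in 2.2.2 include a fatal toxicity, or say which section governs. A separate list of deaths does not correct a Grade 3-4 rate.

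On periods, the reply is that lead-in, overlap and continuation form one regimen, so whole-regimen safety is a proper summary. That is also fair: no section states that periods will be pooled, and pooling follows only because no split is planned. Assignment by onset is imperfect too, since Section 6.1 notes that events may appear months after the last dose. These are reasons to put a period table beside the overall one, not in its place.

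A reader might go further and infer that many non-serious discontinuations will be lost, scaling from the 33% who stopped Sylatron for adverse reactions in the melanoma study. The documents do not support a count. Section 1.3.2 puts the total Sylatron dose here below 20% of that study's median and expects less toxicity. No document gives the share of stops that are non-serious, and 12.4.2 would tabulate them anyway.

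**Conclusion.** The point holds as an inconsistency between sections, and it should be corrected. Followed as written, 2.2.2 leaves a fatal toxicity out of the stated toxicity endpoint. The effect is at most 2.3 percentage points per such patient, assuming 44 patients and worst-grade tabulation. Sections 12.2.2 and 12.4.2 disagree on whether a discontinuation must be serious, the Safety set disagrees with the all-treated population, and no planned summary separates the three treatment periods.

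Two stronger readings should not be drawn. The first is that deaths would go unreported; 12.2.2 and 12.4.2 list them. The second is that the reported toxicity rate is not that of the combination. The time shares cannot show this, because time on treatment is not a share of events and the shares rest on Sylatron stopping at week 12. The documents show only that the planned tables will not let a reader tell the periods apart. Sample size and power are unaffected.

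**What to change.** 1. In Section 2.2.2, replace Grade 3 and 4 with *Grade 3 or higher (3-5)*.
2. In Section 12.2.2, replace the item on serious events with *any adverse event leading to discontinuation of either drug*, to match 12.4.2.
3. Report safety in all treated subjects, as 12.4.2 states, and reconcile this with the Safety set in 12.4 so that patients who leave during the Sylatron lead-in are not lost.
4. Add one table of adverse events by the treatment being received at onset (Sylatron alone, both drugs, pembrolizumab alone) beside the overall table. Defining the periods by treatment actually received keeps the table valid if Sylatron runs past week 12 or is resumed.

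The cost is a wording change in three sections and one extra table. The table needs onset and dosing dates; Section 11.2.1 says only that events go on the eCRF, so confirm that these dates are captured. The toxicity rate may look slightly less favourable. No treatment rule changes.

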2.2.3 Exploratory Endpoints

- The density of CD3 and CD8 in the tumor interior and invasive margin of the tumor, and the clonality of the T-cell repertoire.
- Proliferation of CD8+ T cells, Granzyme B+ cells and proliferation of tumor cells.

3. ELIGIBILITY CRITERIA

This trial is a multi-institutional study, enrolling patients with cholangiocarcinoma, manifesting as either intrahepatic, extrahepatic or gallbladder cancer, that is unresectable, metastatic, or has either failed to respond to or demonstrated progression despite prior therapy. Patients must be, in the opinion of the site investigator, an appropriate candidate for experimental therapy. Patients should be evaluated for the need to undergo biliary drainage by stent placement prior to study participation. Patients should have adequate biliary drainage with no unresolved biliary obstruction.

The target recruitment for this study is 44 patients. As the trial is opening at several centers, recruitment is anticipated to take 21 months, and the anticipated time to complete follow-up of all patients will be 36 months.

3.1 Inclusion Criteria

Subject must meet all of the following applicable inclusion criteria to participate in this study:

1. Be willing and able to provide written informed consent/assent for the trial.
2. Be ≥ 18 years of age on day of signing informed consent.
3. Patients must have received 1 line of prior systemic therapy for metastatic or resectable disease (i.e. patients may have received adjuvant gemcitabine and then later gemcitabine/cisplatin for recurrent metastatic disease)
4. Histological confirmation of cholangiocarcinoma.
5. Have measurable disease based on RECIST 1.1.
6. Be willing to provide tissue from a newly obtained core or excisional biopsy of a tumor lesion. Newly obtained is defined as a specimen obtained up to 6 weeks (42 days) prior to initiation of treatment on Day 1. Subjects for whom newly obtained samples cannot be provided (e.g. inaccessible or subject safety concern) may submit an archived specimen only upon agreement from the sponsor-investigator.
7. Have a performance status of 0 or 1 on the ECOG Performance Scale.

8. Demonstrate adequate organ function as defined in Table 1. All screening labs will be performed within 28 days of registration.

Table 1: Adequate Organ Function Laboratory Values

System	Laboratory Value
Hematological	
Absolute neutrophil count (ANC)	$\geq 1,500 /\mu\text{L}$
Platelets	$\geq 100,000 /\mu\text{L}$
Hemoglobin	$\geq 9 \text{ g/dL}$ or $\geq 5.6 \text{ mmol/L}$ without transfusion or EPO dependency (within 7 days of assessment)
Renal	
Serum creatinine OR Measured or calculated ^a creatinine clearance (GFR can also be used in place of creatinine or CrCl)	$\leq 1.5 \text{ X}$ upper limit of normal (ULN) OR $\geq 60 \text{ mL/min}$ for subject with creatinine levels $> 1.5 \text{ x}$ institutional ULN
Hepatic	
Serum total bilirubin	$\leq 2.0 \text{ X}$ ULN
AST (SGOT) and ALT (SGPT)	$\leq 3.0 \text{ X}$ ULN OR $\leq 5 \text{ X}$ ULN for subjects with liver metastases
Albumin	$\geq 2.5 \text{ mg/dL}$
Coagulation	
International Normalized Ratio (INR) or Prothrombin Time (PT)	$\leq 1.5 \text{ X}$ ULN unless subject is receiving anticoagulant therapy as long as PT or PTT is within therapeutic range of intended use of anticoagulants
Activated Partial Thromboplastin Time (aPTT)	$\leq 1.5 \text{ X}$ ULN unless subject is receiving anticoagulant therapy as long as PT or PTT is within therapeutic range of intended use of anticoagulants
^a Creatinine clearance should be calculated per institutional standard.	

9. Female subject of childbearing potential should have a negative urine or serum pregnancy within 72 hours prior to receiving the first dose of study medication. If the urine test is positive or cannot be confirmed as negative, a serum pregnancy test will be required.
10. Female subjects of childbearing potential should be willing to use adequate birth control or be surgically sterile, or abstain from heterosexual activity for the course of the study through 120 days after the last dose of study medication (Reference Section 5.5.2). Subjects of childbearing potential are those who have not been surgically sterilized or have not been free from menses for > 1 year.
11. Male subjects should agree to use an adequate method of contraception starting with the first dose of study therapy through 120 days after the last dose of study therapy.

3.2 Subject Exclusion Criteria

The subject must be excluded from participating in the trial if the subject:

1. Has symptomatic congestive heart failure, unstable angina pectoris, symptomatic or poorly controlled cardiac arrhythmia. Symptomatic heart failure (NYHA Class II-IV)
2. Has a history of anaphylaxis to peginterferon alfa-2b or interferon alfa-2b
3. Is currently participating and receiving study therapy or has participated in a study of an investigational agent and received study therapy or used an investigational device within 4 weeks of the first dose of treatment.
4. Has a diagnosis of immunodeficiency or is receiving systemic steroid therapy or any other form of immunosuppressive therapy within 7 days prior to the first dose of trial treatment.
5. Has a known history of active TB (Bacillus Tuberculosis)
6. Hypersensitivity to pembrolizumab or any of its excipients.
7. Has had a prior anti-cancer monoclonal antibody (mAb) within 4 weeks prior to study Day 1 or who has not recovered (i.e., \leq Grade 1 or at baseline) from adverse events due to agents administered more than 4 weeks earlier.
8. Has had prior chemotherapy, targeted small molecule therapy, or radiation therapy within 2 weeks prior to study Day 1 or who has not recovered (i.e., \leq Grade 1 or at baseline) from adverse events due to a previously administered agent.
 - a. **NOTE:** Subjects with \leq Grade 2 neuropathy are an exception to this criterion and may qualify for the study.
 - b. **NOTE:** If subject received major surgery, they must have recovered adequately from the toxicity and/or complications from the intervention prior to starting therapy.
9. Has a known additional malignancy that is progressing or requires active treatment. Exceptions include basal cell carcinoma of the skin or squamous cell carcinoma of the skin that has undergone potentially curative therapy or in situ cervical cancer.
10. Has known active central nervous system (CNS) metastases and/or carcinomatous meningitis. Subjects with previously treated brain metastases may participate provided they are stable (without evidence of progression by imaging for at least four weeks prior to the first dose of trial treatment and any neurologic symptoms have returned to baseline), have no evidence of new or enlarging brain metastases, and are not using steroids for at least 7 days prior to trial treatment. This exception does not include carcinomatous meningitis, which is excluded regardless of clinical stability.

11. Has active autoimmune disease that has required systemic treatment in the past 2 years (i.e. with use of disease modifying agents, corticosteroids, or immunosuppressive drugs). Replacement therapy (e.g., thyroxine, insulin, or physiologic corticosteroid replacement therapy for adrenal or pituitary insufficiency, etc.) is not considered a form of systemic treatment.
12. Has known history of, or any evidence of active, non-infectious pneumonitis.
13. Has an active infection requiring systemic therapy.
14. Has a history or current evidence of any condition, therapy, or laboratory abnormality that might confound the results of the trial, interfere with the subject's participation for the full duration of the trial, or is not in the best interest of the subject to participate, in the opinion of the site investigator.
15. Has known psychiatric or substance abuse disorders that would interfere with cooperation with the requirements of the trial.
16. Is pregnant or breastfeeding, or expecting to conceive or father children within the projected duration of the trial, starting with the pre-screening or screening visit through 120 days after the last dose of trial treatment.
17. Has received prior therapy with an anti-PD-1, anti-PD-L1, or anti-PD-L2 agent.
18. Has a known history of Human Immunodeficiency Virus (HIV) (HIV 1/2 antibodies).
19. Has known active Hepatitis B without HBV treatment (HBV infection with ongoing HBV treatment is allowed); has persistent chronic Hepatitis C infection (successfully treated HCV infection is allowed).
20. Has received a live vaccine within 30 days of planned start of study therapy.
NOTE: Seasonal influenza vaccines for injection are generally inactivated flu vaccines and are allowed; however, intranasal influenza vaccines (e.g., Flu-Mist®) are live attenuated vaccines, and are not allowed.
21. Has history of bipolar disorder or major depression as identified by the enrolling physician. See SPM for additional information.
22. Has history of not tolerating interferon treatment.
23. Has known serious neuropsychiatric condition.
24. Has a history of organ or stem cell transplantation

